# Figure 2. Study stop criteria

#### A "Stop" necessitates treatment discontinuation. A study end visit may be conducted after a "Stop" if necessary (i.e. midway through sessions).

#### Screening:

Participants for all groups will be recruited from the NYU Langone Medical Center Multiple Comprehensive Care Center. Once a potential participant is identified, a screening phone call will take place to determine general eligibility (See section IX. Consent Process). Once a participant is deemed generally eligible, the individual will be scheduled for a visit at NYU to review and sign consent and complete screening procedures, including a medical clearance. For those interested in study participation, once eligibility is confirmed by a NYU MS Center clinician, their baseline appointment will be scheduled.

#### **Baseline Visit**:

#### \*Note clinician assessment for medical clearance may occur either before or at the baseline visit

All women who are of child-bearing age will complete a pregnancy test (human chorionic gonadotrophin urine assay) to assure they are eligible for all study procedures. Women who receive a result denoting heightened hCG levels will be considered study screen failures.

Prior to tDCS training, the tests and evaluations detailed in Table 2 will be administered.

#### tDCS aptitude screen and tolerability test:

• **tDCS Aptitude**: Participants will first complete an aptitude test to confirm that they have the cognitive and motor skills required for headset placement. With instruction of the study technician, they will be asked to insert the sponges onto the headset and place the electrodes into the sponges. The technician will determine whether or not the participant is qualified to proceed. Participants will not be allowed to proceed if they are not able to correctly either 1) attach sponges to headset or 2) place electrodes into the sponges.

**tDCS Tolerability:** The study technician will next directly place the headset and then initiate a one-minute test session, with 30 seconds of ramp-up to target, followed by a 30-second ramp down. The tolerability test will first take place using 2.5 mA stimulation. If the participant tolerates and agrees, 2.5 mA will be used for all following stimulation sessions. Alternatively, if the participant cannot tolerate 2.5 mA, stimulation will be based on highest amplitude tolerated, following 0.5 mA decrements (2.0, 1.5., and 1.0 mA.) till finally a base 1.0 mA stimulation is offered. Once the tolerable dose is established, it will remain constant throughout the study. If the participant cannot tolerate any of the offered stimulation levels, they are excluded from the study.

# **Remotely Monitored Study Sessions 2 to 40:**

These sessions will be completed from home with remote monitoring by the study technician. For participants in the sham condition who elect 10 additional sessions of the open-label, active tDCS, these same procedures will be repeated.

Participants will schedule times during which they are certain they can self-administer the tDCS while they are being remotely monitored by study staff. They will be observed using a secure internet-based video chat program that will be installed in the laptop they will use for the study. To start their session, the participant will connect to study staff via a secure internet-based video program.

They will put on the tDCS headgear while being monitored, and tell study staff if the device feedback indicates that the electrodes are acceptably placed. The participant will then receive the activation code from the tDCS device. If the study staff observes the participant making any errors that may cause the latter discomfort they can intervene with instructions for correction.

# Safety notes:

- The tDCS device can only operate if: 1) the headset is correctly placed for adequate connection, and 2) the study technician provides a session code that unlocks the device for a one-time only 20 minute period of use.
- If the device loses adequate contact for any reason, the device will automatically discontinue the session. The session can only be reestablished if another unlock code is provided by the study technician.
- If the participant wishes to discontinue the session at any time, they will be instructed to press the "abort" key which ramps down the current within 30 seconds to allow for headset removal.

# **Study End Visit:**

Within three days of their last session (including same day), participants will have their final study end visit in clinic. The tests and evaluations administered at baseline will be given to the participant again (Table 1). The equipment that had been provided to the participant for this study will be returned on this visit.

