electrode site and include itching, tingling, and burning. Initial studies have found tDCS to be effective in a variety of uses in healthy participants as well as in a range of clinical conditions and may be preferred to drug treatment in special populations (such as pregnant women) due to its safety advantages.

tDCS is considered especially promising for symptomatic treatment in MS both for its tolerability, deployability (based on our innovative remotely-supervised approach), and presumed mechanism of action. While there is emerging study the cellular mechanisms of tDCS, what is established is that sustained (minutes) of tDCS can produce lasting changes in brain excitability and that these changes are plastic and cumulative with repeated sessions . One of the largest and more reproducible effects in healthy volunteers is enhanced vigilance with an increased ability to engage selective attention, a finding which may indirectly underpin the cognitive benefits of tDCS. In clinical populations, one of the most replicated measures is elevated mood and has been considered an effective treatment for depression.

We have developed a telemedicine tDCS protocol that will facilitate recruitment, increase compliance, and enable designs with multiple sessions to evaluate benefits of a cumulative effect. tDCS urgently requires further study to fully leverage this treatment modality for maximal clinical benefit in MS. Repetitive sessions are necessary to produce cumulative effects as shown in neurophysiology studies and clinical trials for neuropsychiatric disorders and rehabilitation. For the treatment of depression, a clinical application that has received extensive study, some patients have required 20 to 30 sessions or more for optimal improvement .

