# **Specific Aim 2:** To test the preliminary efficacy of tDCS to treat fatigue and to enhance outcomes of cognitive training. These data will inform the design of a large, controlled clinical trial.

The *primary outcome* will be comparisons between the active and control conditions on measures of fatigue and cognitive functioning.

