# e)Analytic Plan:

Specific Aim 1 is to determine feasibility; to be measured by the number of participants successfully completed using the proposed protocol for training and monitored administration. As would be expected, there is a high rate of compliance for in-clinic tDCS administration and therefore remotely-supervised administration should be designed to be similarly compliant. Study success will be defined by 80% participants having completed 80% sessions, shown to be the target compliance for previous tDCS studies. We will also determine the effectiveness of our sham procedures to ensure blinding, as tested by comparing those who accurately identified the sham condition. We will assess whether the frequency or type of side effects differ between the active and control conditions and whether they occur at the same rate as reported from studies of in-clinic administration. Secondary outcomes will be tolerability, participant-reported adverse events, and comparisons of active and control conditions on these measures.

Specific Aim 2 will be to determine preliminary signals for efficacy, and to have pilot findings to determine necessary sample sizes for an adequately-powered clinical trial. For each participant, change scores will be calculated between baseline and study end scores on measures of fatigue and cognitive functioning. These difference scores will then be described and compared between groups (t-tests and ANOVA related analyses) to determine signals of efficacy for active tDCS paired with cognitive remediation vs. active tDCS paired with non-adaptive puzzle and board games vs. sham tDCS paired with cognitive remediation.

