The safety of this technique has been addressed and tested by multiple researchers (e.g., Hummel, et al.; Fregni, et. al.; Nitsche, et al.; Priori, et al.) who have concluded that tDCS, as applied in a manner similar to our proposed protocol, induces only temporary mood, cognitive / motor effects, and no negative side effects. For example, researchers at the National Institute of Neurological Disorders and Stroke (NINDS), Iver et al. conducted a safety study on tDCS, investigating 20-minute sessions of 1 mA and 2 mA current stimulation with healthy controls (n=103). No negative effects were identified. Nitsche and colleagues found no measurable structural changes in brain tissue due to tDCS. In a meta-analysis of over 200 tDCS studies conducted from 1998 to 2010, 56% of studies mentioned adverse events, which were generally minor. The most commonly reported side effects included itching, tingling, headache, burning sensation and discomfort limited to the scalp site where the tDCS electrodes were applied. To date, there have been no reports of seizures induced by tDCS. Importantly this is the case in normal volunteers, but also in different populations of patients, including patients with disorders where there might be an increased risk of seizures (e.g. Alzheimer's disease, recent stroke, epilepsy). A study from NYU on the use of tDCS in patients with epilepsy encountered no increase in complications of tDCS in the patients as compared with controls. Specifically, there were no instances of seizures induced by tDCS.

Participants in all groups may find the questionnaires time consuming and potentially bothersome. Neuropsychological testing and the computer training sessions may, in some individuals, be stressful or anxiety producing. There is a small risk of loss of confidentiality. Participants will be assigned a study ID and their name will not be used on any of the information collected. The program used for brain training games will not collect any personally identifiable information. The results of these data collected may be used for publication but will not include the participants' names. Hardcopies of the data files will be kept in secure, locked files and data will be entered in a secure, NYU approved database

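### With same-day study-end testing allowed, the active-versus-sham change score can mix a transient after-effect of the last session with sustained benefit

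*Combined protocol and SAP*

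**What the plan says.** The two ends of the Aim 2 change score are taken under different conditions.

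- **Baseline** (section VI, Baseline Visit): "Prior to tDCS training, the tests and evaluations detailed in Table 2 will be administered". These scores are free of stimulation.
- **Study end** (section VI, Study End Visit): "Within three days of their last session (including same day), participants will have their final study end visit in clinic". There is no lower limit in hours.
- **Analysis** (section V, Analytic Plan, repeated in section IX, Statistical Analyses): "change scores will be calculated between baseline and study end scores on measures of fatigue and cognitive functioning", then compared between arms by t-tests and ANOVA-type methods. Neither section has a term or sensitivity analysis for time since the last session.
- **Aim** (section IV, Specific Aim 2): "To test the preliminary efficacy of tDCS to treat fatigue and to enhance outcomes of cognitive training". The results are to guide the design and sample size of a larger trial.

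On what stimulation does, section II says: "One of the largest and more reproducible effects in healthy volunteers is enhanced vigilance with an increased ability to engage selective attention". It adds that this may indirectly underlie the cognitive benefits. Section X (Risk to Participants) reports that stimulation applied much as in this protocol "induces only temporary mood, cognitive / motor effects, and no negative side effects". Neither place gives a size or duration.

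Table 2 also marks the tDCS tolerance test at study end as well as at baseline. The Study End Visit section does not say whether it comes before or after the battery.

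**The concern.** Someone tested on the day of the last session may still carry a short-lived effect of that session. Someone tested three days later may not. The baseline score carries none in either case.

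Randomisation does not remove this from the comparison with sham. Under section VI, sham delivers current only during brief ramps at the start and end of the session, so an acute effect of active current would fall on one side. Section IX attaches its main cognitive hypothesis, a gain at least one normative SD larger than under sham, to that same contrast.

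What is at stake is the meaning of the pilot estimate. If part of an active-versus-sham difference is transient, a later trial sized on it as a lasting benefit would be too small.

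**Working it through.** The plan states no figure on this point, so there is none to reproduce. The check has two parts.

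**1. Which contrasts and measures are exposed**

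| Contrast or measure | Position |
|---|---|
| Active + remediation vs sham + remediation | Exposed: only one arm has full active current |
| Active + remediation vs active + games | An additive acute effect cancels if visit timing is similar in both arms |
| Performance tests (SDMT, Attention Network Test, Cogstate) | Most exposed: the one-month survey repeats no cognitive test except delayed word recall |
| Visual-analog fatigue and brief mood ratings | Partly covered: section V and Table 2 collect them before and after each session |
| Fatigue and mood questionnaires | Partly covered by the one-month survey, which is outside the Aim 2 change score |

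**2. Possible size (illustration)**

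Inputs: f, the share of active participants tested while the effect persists, and a, the acute effect in SDs of the change score. The documents give neither. Assumed ranges are f = 25-75% and a = 0.2-0.4.

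Bias in the active-minus-sham difference = f × a.

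- Low: 0.25 × 0.2 = 0.05 SD
- High: 0.75 × 0.4 = 0.30 SD
- Nobody tested the same day: 0 × a = 0

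For scale, section IX plans for 15 analysed per arm. Full enrolment gives 85/3 ≈ 28. With unit SD, the standard error of the difference is √(2/n): √(2/15) = 0.37 and √(2/28) = 0.27.

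With no lasting effect, the chance of a two-sided p < 0.05 is Φ(b/SE − 1.96) + Φ(−b/SE − 1.96), where b is the bias. The plan states no alpha, so 5% is assumed.

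| Bias | 15 per arm | 28 per arm |
|---|---|---|
| 0 | 5.0% | 5.0% |
| 0.05 SD | 5.2% | 5.4% |
| 0.30 SD | 13.0% | 20.2% |

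For the next trial, required sample size varies as 1/d². If the lasting effect were 1 SD and the pilot showed 1.05 or 1.30, the next trial would be too small by a factor of 1.05² = 1.10 or 1.30² = 1.69. This treats the hypothesised normative SD and the SD of change as the same unit, which the plan does not establish.

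Unequal intervals add little noise. With a = 0.4 and f = 0.5, the added variance is 0.4² × 0.5 × 0.5 = 0.04, which raises a unit SD to √1.04 = 1.02.

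**The case against.** A reader might infer that after-effects of the last session are being counted as the cumulative benefit Aim 2 sets out to measure. The documents do not support that. Same-day testing is permitted, not required, and the share tested that day is unknown. The cumulative wording ("enable designs with multiple sessions to evaluate benefits of a cumulative effect") is in the Background. Aim 2 asks only for preliminary efficacy, and status at end of treatment is a legitimate pilot outcome.

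A reader might also infer that every Aim 2 comparison is affected, or that transient and lasting effects could not be separated for any outcome. Neither follows. The two active-current arms share the acute effect. For visual-analog fatigue, pre-session ratings track change without same-day stimulation, and post-minus-pre differences estimate the acute effect. That analysis is not planned, but the data for it are collected.

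The evidence for carry-over is also thin. The vigilance statement concerns healthy volunteers. The Background further describes lasting excitability changes that build up with repetition, so the documents do not show that day 0 is affected while days 1 to 3 are clean. Direction is uncertain too: tiredness that is greater after active than after sham sessions would lower same-day performance and bias against active treatment. Tiredness common to both arms would cancel. Finally, the assumed maximum of 0.30 SD is below one standard error (0.37) at 15 per arm.

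All of this stands and limits the point. What remains is that the plan allows one end of its main contrast to follow stimulation by hours and has no means of checking whether that matters for the performance tests.

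**Conclusion.** The point holds in limited form, as a cheap improvement rather than a flaw that undermines the trial. The 0-to-3-day window has no minimum gap, and time since stimulation is neither fixed nor analysed. Active-versus-sham results on performance tests can therefore mix a transient effect, of a kind the protocol itself describes, with a sustained one.

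The 0.05-0.30 SD range rests wholly on the assumed share and acute effect. It also assumes that the effect is additive, favours active current, and has gone by the next day. The documents confirm none of these.

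**What to change.** In section VI, Study End Visit:

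1. Remove the same-day allowance for the efficacy battery, so that it is given one to three days after the last session in all arms.
2. State that the study-end tolerance test in Table 2 follows the battery.
3. Record hours between last stimulation and testing.

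In section IX, add a sensitivity analysis of the active-versus-sham change scores by interval. The interval is not randomised and the arms are small, so this should be descriptive. The pre/post-session fatigue and mood ratings and the one-month questionnaires can serve as supporting evidence.

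Testing before that day's session is not a good substitute. Sessions 2 to 40 take place at home and the equipment is returned at the study-end visit, so a session after the battery would need new arrangements.

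The tests, the visit and the three-day outer limit stay as they are. The cost is a few sentences, one recorded time and slightly less scheduling flexibility. A one-day gap may not clear every after-effect, which is why the interval should also be recorded.

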#### **Online/TelephoneSurvey:**

One month following the study end visit, participants will receive an online survey to complete through REDcap. This survey will consist of a text box to enter delayed recall words from the RAVLT task completed at follow-up, as well as the Multiple Sclerosis Neuropsychological Questionnaire (MSNQ), PROMIS Measure of Fatigue, Mood and Health-Related Quality of Life, Neuro-Quality of Life measures, the Fatigue Impact Scale, the Fatigue Severity Scale, and the Positive and Negative Affect Scale (PANAS). In addition to these 7 measures, participants will be asked to assess their experience with the study:

"Overall, did you feel a benefit from participating in this trial? If so, how? If so, has the benefit lasted?"

All data will be entered into REDcap, either directly by participants if they select to complete the measures online, or by research assistants if the participants select to complete the measures in an interview format via phone.

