Of the eight published trials of tDCS to date, three have directly targeted fatigue. As shown in **Table 1**, all three have used sham-controlled crossover designs, and found significant improvement in fatigue following active treatment in either the full group or subset analyses. Each of the three studies varied in their montage with similar results.

Table 1 . tDCS studies of fatigue in MS to date, including our feasibility study and proposed study							
Author (Year)	Sample n	Design	#Sessions, Treatment Montage				
Ferrucci et al. (2014) 	25	Sham-controlled crossover	5 sessions x 1.5 mA motor cortex x 15 minutes				
Saiote et al. (2014 ) 	13	Sham-controlled crossover	5 sessions x 1.0 mA DLPC x 20 minutes				
Tecchio et al. (2014) 	10	Sham-controlled crossover	5 sessions x 1.5 mA x 15 minutes; sensorimotor cortex				
Protocol feasibility study	17	Open-label (remote protocol)	10 sessions x 1.5 mA DLPFC x 20 minutes				

Two of the three studies included analyses to link to the mechanism of benefit, with unclear results. Saiote et al. included MRI and found a correlation between lesion load in left frontal cortex and reduced fatigue following tDCS treatment. In a follow-up second analyses, Tecchio et al. found tDCS treatment was more effective against MS fatigue when the electrode was focused on the bilateral whole body somatosensory area (but changes in S1 and M1 excitability did not correspond to treatment benefit).

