#### A pilot study of remotely-delivered (tDCS) combined with cognitive training in adults with multiple sclerosis (MS) (S15-01189)

fatigue (pre- and post-								
Visual analog scale for pain (pre-, early-, mid- and post-session)		Х	X	X	X	X		
Tolerability questionnaire - administered by study staff (pre- and post-session)			X		X			
Safety and tolerability questionnaire –self-report (pre- and post-session)			X		X			
Score for Computerized cognitive games (daily)*			Х		Х			
Daily assessment of sleep			Х		X			
Patient and Caregiver Questionnaires*						Х		
Participant Evaluation of Study Procedures*			Х	Х	X	Х		
Count of successful tDCS sessions (confirmation code by session days)			X	X	X	X		
Optional measures that may b	e exclude	d based on s	tudy persor	nel judgem	ent are indicat	ed by an aster	risk.	

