An adverse event is defined as any rating (at any time) of pain of greater than "moderate" or side effects or sensations that arise preceding, during, or following stimulation. Pain and tolerability are measured before, during and after each session. As noted, there is an extensive body of literature demonstrating the safety and tolerability of tDCS both in MS and in a range of clinical disorders. Our lab at Stony Brook Medicine administered >200 active tDCS sessions to MS participants with no pain ratings of severe or greater and no discontinued session (for any reason, safety or tolerability). Figure 3 below demonstrates these results.

Figure 3. Self-applied tDCS sessions across n=20 participants

We will submit study data safety monitoring reports to the IRB after 10 participants are enrolled in the active condition, and follow with reports for each further increment of 10 active enrollees.

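### No side-effect question is scheduled after the last session's form, while the one-month survey asks directly about lasting benefit

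*Combined protocol and SAP*

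**What the plan says.** Two rows of Table 2 (Study Outcome Measures) ask about side effects. One begins "Tolerability questionnaire - administered by study staff (pre- and post-session" and the other "Safety and tolerability questionnaire –self-report (pre- and post-session". Both are ticked under the two daily-session columns and nowhere else. Table 3, for the PD cohort, ticks them in its daily-session column only.

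The Study End Visit section sets the timing: "Within three days of their last session (including same day), participants will have their final study end visit in clinic". It repeats the baseline tests, and neither questionnaire is ticked at baseline.

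The Online/Telephone Survey section, one month later, lists word-list delayed recall, six symptom, mood and quality-of-life measures, and one experience question: "Overall, did you feel a benefit from participating in this trial? If so, how? If so, has the benefit lasted". The PD section takes over the same methods, with some additions in Table 3.

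The Monitoring section counts as adverse events "side effects or sensations that arise preceding, during, or following stimulation", without saying when collection ends. It describes tolerability as measured before, during and after each session.

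**The concern.** Tolerability and participant-reported adverse events are named secondary outcomes of Specific Aim 1 and of the PD Exploratory Aim, and the PD hypothesis is that the treatment is safe and feasible. The natural time to ask about effects of a whole course is after it ends, and at that point the two side-effect forms stop. A symptom that arises after an earlier session can be caught by the next pre-session form. After the last session there is no next form.

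The one open question afterwards is one-sided. A participant with a lasting benefit is asked about it. A participant with a lasting scalp irritation or headache has to raise it unprompted. Anything written about participants' later experience would lean towards benefit because of the wording.

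**Working it through.** **Step 1: what is scheduled after the course.** Read from Tables 2 and 3 and the survey section:

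| Item | Last session | Study End | One month |
|---|---|---|---|
| Staff tolerability questionnaire | yes | no | no |
| Self-report safety and tolerability questionnaire | yes | no | no |
| Pain visual analog scale | yes | yes | no |
| PROMIS, Neuro-Quality of Life, MSNQ, Fatigue Impact and Fatigue Severity Scales | no | yes | yes (optional in MS) |
| PANAS | yes (optional in MS) | yes (optional in MS) | in the survey text, not ticked in either table |
| UPDRS, CG S/I, PDQ-39 (PD only) | no | yes | yes (UPDRS Part 2 only) |
| Experience question | no | no | benefit only |

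Side-effect questionnaires scheduled: 0 of 2 at Study End and 0 of 2 at one month, in both cohorts.

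**Step 2: what remains uncovered.** The scales cover fatigue, mood, self-reported cognition and quality of life, plus daily living in PD. Pain is covered to Study End. No listed item asks about skin effects, headache or any other side effect.

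**Step 3: what asking would buy.** The plan gives no figure here, so the size is shown as a zero-event bound. If *n* people are asked and none reports an effect, the one-sided 95% upper limit for its frequency is 1 − 0.05^(1/*n*).

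- Active MS participants: two of three arms at 1:1:1, so 85 × 2/3 = 56.7, about 57. Limit: 1 − 0.05^(1/57) = 5.1%.
- With the 33% dropout that Statistical Analyses allows, taken here as an assumed non-response rate: 57 × 0.67 = 38.2, about 38. Limit: 1 − 0.05^(1/38) = 7.6%.
- PD, all 30 responding: 1 − 0.05^(1/30) = 9.5%.

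With nobody asked, *n* = 0 and no limit exists for the uncovered effects.

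**Step 4: which contact supports a comparison.** The Open label tDCS Sessions section offers active stimulation to the sham arm after the study end visit. Study End therefore precedes that crossover. By one month some sham participants may have had up to 10 active sessions.

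**The case against.** The strongest reply is that follow-up is broader than the two forms suggest. This is largely right. The experience question is added to seven measures, six of which can worsen as well as improve. Pain is rated at Study End, and the Monitoring section counts any pain rating above moderate, at any time, as an adverse event. The weekly team review covers clinical course and medical records. Study End also has patient, caregiver and procedure-evaluation questionnaires in MS, although they are optional and their content is not given. A reader might infer that the survey asks about nothing but benefit, or that the trial cannot detect lasting harm. The documents support neither. They also do not support confining the safety data to the hours around each session, because pre-session forms span the course.

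This cover still has limits. In Table 2 every scale ticked at one month may be omitted at staff discretion, and no listed measure asks about side effects as such.

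Second, the Risk to Participants section says that effects such as tingling and redness disappear once stimulation stops, so session-linked collection is a deliberate choice. That explains the design, but asking after the course would test the statement directly. The Background remark that "these changes are plastic and cumulative with repeated sessions" concerns brain excitability, so it is not evidence of cumulative side effects.

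Third, a reader might use exposure to size the gap. The feasibility study gave "10 sessions x 1.5 mA DLPFC x 20 minutes", or 300 mA-minutes, against up to 40 × 20 × 2.5 = 2,000 in MS, which is 6.7 times. This shows only that the pilot does not cover the planned MS exposure. It does not measure what follow-up misses, and it does not carry over to PD: 10 × 20 × 2.5 = 500, or 1.7 times.

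Finally, the contrast with benefit should not be overdrawn. The efficacy analysis runs from baseline to study end, and no one-month analysis is described. Open-label treatment weakens any one-month comparison of arms, for benefit and harm alike.

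**Conclusion.** The point holds in a bounded form. After the last post-session form, no side-effect or adverse-event question is scheduled in either cohort, and the one-month experience question asks about benefit alone. The gap is persistent or delayed effects outside the domains in Step 2, for which the plan relies on volunteered reports.

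Nothing here shows that such effects occur. The limits of 5.1% to 7.6% in MS and 9.5% in PD describe what a clean result could support if the question were asked. They assume zero reports, independent participants and a form that would pick up the effect. They depend on the number who answer, and 5.1% and 9.5% require everyone to respond. This is an ascertainment gap worth closing. It does not undermine the session-level tolerability data.

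**What to change.** 1. In Tables 2 and 3, tick the existing self-report safety and tolerability questionnaire at Study End and at the one-month survey. Ask about any symptom that is new, worse or still present since the sessions ended. Restricting it to new or worse symptoms would miss effects that began during treatment and persisted.
2. Reword the survey item neutrally, for example: *Did you notice any benefit or any unwanted effect? If so, what, and has it lasted?*
3. Make the between-arm comparison at Study End, before open-label sessions start. Report one-month answers descriptively, by current actually received and including open-label sessions, with the number responding.
4. Base any zero-event limit on the number who respond.
5. Send any report of an unwanted effect to the existing weekly review.

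The cost is a few minutes per participant at two contacts already planned, and some unrelated symptoms to sort. No new visit or staff is needed.
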